#### **4.1. Statistical analysis**

Demographic and patient-reported results in the study will be summarized with descriptive statistics. Continuous, normality checks of measurements will be tested with the Shapiro Wilk test. Differences in repeated measures between groups will be tested with the Repeated Measures test (repeated measure analysis of variance). Bonferroni test will be used for pairwise comparisons. Differences between groups for each measurement will be tested with the Independent Samples t-test. Number and percentage values will be given as descriptive statistics. Pearson chi-square and Fisher Exact chi-square tests will be used for differences between categorical variables. Number and percentage values will be given as descriptive statistics. P<0.05 will be taken as statistical significance.

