#### **4.2. Research Design: Prospective**

#### **4.3. Design of the Research**

The population of the research will be hemodialysis patients treated at Adana City Hospital between 30 May 2023 and 30 September 2023. The research sample will consist of patients who meet the research criteria and agree to participate voluntarily in the research. The sample number of the study was calculated using the G\*Power 3.1.9.7 program (25). In the calculation, a sample calculation was made for repeated measures ANOVA test. In the calculation, Cohen's medium effect size ( $f = 0.5$ ), 5% margin of error ( $\alpha = 0.05$ ) and 95% power ( $1-\beta = 0.95$ ) and the correlation value between repeated measurements were taken as 0.50 for each group (study and control). ) sample size was calculated as 21 patients (42 patients in total). Considering the possibility of patients leaving the groups during the research process, the number of samples for each group was increased by 30%, taking into account the possibility of data loss in order not to adversely affect the statistical power, and 30 patients (total of 60 patients) for each group (study and control) were included in the sample planned (26). Randomization in the study will be done on the website of randomizer.org and patients will be included in the study and control groups with the appropriate randomization method according to the dialysis unit list (27).

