#### **F tests - ANOVA: Repeated measures, between factors**

**Analysis: A priori: Compute required sample size**

**Input:**

Effect size f	= 0.5
<math>\alpha</math> err prob	= 0.05
Power (1-<math>\beta</math> err prob)	= 0.95
Number of groups	= 2
Number of measurements	= 2
Corr among rep measures	= 0.5

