**Output:**

Noncentrality parameter <math>\lambda</math>	= 14.000000
Critical F	= 4.0847457
Numerator df	= 1.000000
Denominator df	= 40.000000
Total sample size	= 42
Actual power	= 0.9545279

In the study, 60 hemodialysis patients were randomly assigned to the study and control groups. The study group (n=30) Acupressure is formulated according to the standards of the World Health

[figure not shown]
**NCT Number:** 05892679

Organization and in a certain order to the points of Stomach 36 (St 36), Gall Bladder 34 point (GB 34), Spleen 6 point (SP 6) and Kidney 1 point (K 1) will be applied. Consideration will be given to the appropriate pressure intensity and duration. Since the reactions of individuals will be different from each other, the stiffness and pressure will be adjusted according to the sensitivity of the individual in order not to cause tissue damage. Pressures will be applied manually by a single practitioner. Considering the anatomical area where the point is located, the most suitable thumb, index and/or middle finger will be used for application to the relevant point. Successive compressions will be applied at a frequency that does not disturb the patient, does not cause pain, and has a calming effect.

Considering the studies done, a person will be given acupressure three times a week for four weeks. No intervention will be made to the control group (n=30). In order to avoid ethical problems both groups will be given an informative training on acupressure and fatigue, increase the quality of life and comfort level in hemodialysis patients at the end of the study. The primary outcome of the study is the effect of acupuncture on fatigue in hemodialysis patients. The secondary result of the study is the effect of acupuncture on quality of life and comfort level in hemodialysis patients.

[figure not shown]
[figure not shown]
The results will be collected before the acupressure and in the 4th week of the last intervention.

Table 1. Application Points Used in the Study (33)

Application Site Name	Picture of Application Site	Description of Application Site
Stomach 36. point  (Zusanli: ST 36)		In the leg, it is one finger width lateral to the anterior crest of the tibia, and 3 cuns below the ST 35 in the depression on the lateral side of the patella.

**NCT Number:** 05892679

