## 5. Research Flow Process

The Flow Chart of this research will be completed in three stages and four steps as indicated in Figure 1.

**First Stage (Preparatory Stage):** An internationally approved acupressure certificate was obtained by the researcher in July 2022 (the certificate is in Annex I). The place where the acupressure application will be made will be arranged in accordance with the acupressure application. Necessary materials will be purchased for acupressure application (bed cover, pillow, etc.)

**Second Stage (Implementation Stage):** This stage will consist of four steps.

**In the first step:** In the first step of the application, patients who receive hemodialysis treatment in Adana City Hospital dialysis unit and meet the research criteria and are willing to participate in the research will be given brief information about the research and their verbal consent will be obtained. The fatigue experience VAS scores of the patients who accepted to participate in the study on a voluntary basis will be calculated. Those with a VAS value of fatigue severity  $\geq 4.0$  between 0 and 10 points will constitute the sample of the study.

**In the second step:** Sample selection will be completed in accordance with the inclusion, exclusion and exclusion criteria of the study, and then randomization will be performed. The patients will be informed about the purpose of the research and the research process, and the patients will be asked to fill in the "Piper Fatigue Scale", "Kidney Disease and Quality of Life Form" and "Hemodialysis Comfort Scale" as a pre-test with an informed consent form.

**Third step:** Patients in the study group will be given a total of 12 sessions of acupressure application bilaterally to Stomach 36 (St36), Gall Bladder 34 (GB34), Spleen 6 (SP6) and Kidney 1 (K1) acupuncture points for 4 weeks and 3 days a week for 20 minutes. No intervention will be made to the control group other than routine maintenance during the four-week period.

**Fourth step:** After the 4-week acupressure process is over, after the last acupressure session, the patients in the study group will have the "Piper Fatigue Scale", "Kidney Disease and Quality of Life Form" and "Hemodialysis Comfort Scale" filled face-to-face as a post-test. At the end of 4 weeks, the control group will have to fill in the "Piper Fatigue Scale", "Kidney Disease and Quality of Life Form" and "Hemodialysis Comfort Scale" as a post-test before hemodialysis.

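### Nothing says that patients who stop acupressure early still complete the week-4 forms, so loss related to fatigue can bias the comparison; the 30% allowance protects power only

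*Combined protocol and SAP*

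**What the plan says.** - **Outcome.** Section 4.3, after the sample size output: "The primary outcome of the study is the effect of acupuncture on fatigue in hemodialysis patients" (the intervention is acupressure). The Piper Fatigue Scale is completed at pre-test and post-test.
- **Analysis.** Section 4.1: "Differences in repeated measures between groups will be tested with the Repeated Measures test (repeated measure analysis of variance") and "Differences between groups for each measurement will be tested with the Independent Samples t-test". The section names no analysis set, no rule for missing post-tests and no sensitivity analysis.
- **Timing.** The text before Table 1 says "The results will be collected before the acupressure and in the 4th week of the last intervention". For the study arm, the fourth step in section 5 (Research Flow Process) says "After the 4-week acupressure process is over, after the last acupressure session, the patients in the study group" complete the forms. The control arm completes them when 4 weeks have passed. Figure 1 repeats both timings.
- **Loss.** Section 4.3: "Considering the possibility of patients leaving the groups during the research process, the number of samples for each group was increased by 30" per cent, giving 30 per arm instead of 21. The stated purpose is to protect statistical power.

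**The concern.** Only the study arm has sessions to abandon: 12 of them over four weeks. If its post-test follows the last session and nothing covers a patient who stops in week 2, that patient may never be measured. A control patient only has to be present when 4 weeks have passed. With one follow-up value, a patient without it drops out of the planned tests.

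The groups compared may then no longer be the groups randomised. Fatigue is self-reported and controls receive routine care only, so patients who feel no better could plausibly be the ones who stop. The remaining study-arm patients would then look less fatigued even if acupressure did nothing. Enrolling more patients does not correct this.

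**Working it through.** **1. The plan's sample size.** Inputs from section 4.3 and its G*Power output: f = 0.5, alpha 0.05, 2 groups, m = 2 measurements, rho = 0.5, N = 42, for the test labelled "ANOVA: Repeated measures, between factors".

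λ = f²·N·m / (1 + (m − 1)·rho) = 0.25 × 42 × 2 / 1.5 = 14.0. Critical F(1, 40) = 4.0847 and power = 0.9545. All three match the stated output.

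**2. The allowance.** 21 / (1 − 0.30) = 30 per arm, as planned, whereas 21 × 1.30 = 27.3 would give 28. The 30 therefore corresponds to losing 30% of those randomised: 9 per arm, leaving the 42 of step 1 at power 0.9545. If all 60 are measured, λ = 0.25 × 60 × 2 / 1.5 = 20 and power is 0.9926. Power is covered in both cases.

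**3. Bias if loss depends on post-test fatigue.** Assumptions not in the documents: no true effect; normal scores with SD 1 at each time; 30% loss in each arm; control loss random; study-arm tendency to leave correlated r with post-test fatigue. rho = 0.5 is the plan's value.

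The shift in the study-arm completers' post-test mean is −r·φ(z)/(1 − L). With L = 0.30 the factor φ(z)/(1 − L) is 0.497. For r = 0.5:
- post-test: −0.5 × 0.497 = −0.248
- baseline: rho × (−0.248) = −0.124
- change (the group-by-time test): −0.248 + 0.124 = −0.124
- mean of the two times (the between-groups test that was sized): (−0.248 − 0.124)/2 = −0.186
- ANCOVA, approximately: −0.248 + 0.5 × 0.124 = −0.186

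False-positive rates from 20,000 simulated null trials, nominal 5%:

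| Test | Bias (SD, toward acupressure) | False positives |
|---|---|---|
| Change | 0.12 | 7% |
| Post-test t-test | 0.25 | 12 to 13% |
| Between-groups effect | 0.19 | 11% |
| ANCOVA on completers | 0.19 | 11% |

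**4. Range.** For r = 0.3 to 0.7, the bias is about 0.07 to 0.17 SD in change (false positives 5.7% to 8.7%) and 0.15 to 0.35 SD at post-test. With 10% loss the change bias is 0.03 to 0.07 SD. With r = 0, or with all 60 measured, there is no bias and false positives are about 5%.

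**5. Loss that depends on baseline fatigue instead (r = 0.5).** The baseline mean shifts by −0.248 and the post-test mean by 0.5 × (−0.248) = −0.124. Change is then +0.124, against acupressure. The post-test t-test is biased by 0.124 toward it. ANCOVA gives −0.124 + 0.5 × 0.248 = 0.

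**6. Precision.** With random loss to 21 per arm and an assumed post-test effect of 0.7 SD, power is about 71% for ANCOVA, 60% for the change test and 25% for the between-groups test.

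**The case against.** The plan does not say that early stoppers are dropped. Figure 1 shows n = 30 in the study arm at the post-test step. The fourth step speaks of the study group's patients, not of those who finished 12 sessions, and it also says the 4-week process must be over, which is partly a calendar anchor. The 30% is an allowance for a possibility, not a forecast, and no reasons for leaving are given.

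All of this stands. It rules out several stronger readings that a reader might infer:

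- **That the plan specifies a completers-only analysis.** It is silent. A completers comparison is what results by default if early stoppers are not measured.
- **That a large false-positive rate should be expected.** If the nine study-arm patients with the worst week-4 scores all leave while control loss is random, false positives reach about 14% for the change test and 36% for ANCOVA on completers. The documents do not support so extreme a pattern.
- **That any bias must favour acupressure.** Step 5 of the working shows that the change test can be biased the other way.
- **That a better model cures the problem.** With a single follow-up value and only baseline as predictor, ANCOVA with multiple imputation or a mixed model gives essentially the completers' ANCOVA answer. When loss depends on the outcome, that can be more biased than the change test (0.39 against 0.25 SD in the extreme pattern).

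The objection does not supply the missing rule. No section says that a patient who stops sessions is still measured at week 4, or who is analysed.

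**Conclusion.** The gap is real and should be closed. As written, the plan can lead to a comparison of completers, and its only provision for loss protects power. Bias arises only if loss is related to fatigue and differs between the arms. In the middle case examined it is about 0.12 SD in change and 0.25 SD in the post-test t-test. These sizes rest on assumed loss mechanisms and on 30% actually being lost; smaller or random loss gives little or no bias. The documents do not show that such loss will occur or which way it would act. The main remedy is follow-up of every randomised patient; the choice of model comes second.

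**What to change.** 1. **Fourth step and Figure 1.** State that the three forms are collected at the week-4 dialysis session, defined identically in both arms, from every randomised patient who has not withdrawn consent, whatever number of acupressure sessions was received. This removes the bias from patients who stop sessions but can still be measured.
2. **Section 4.1.** Make the primary fatigue analysis an ANCOVA of the week-4 Piper score on group and baseline Piper score, with patients in their assigned group. This gains precision and removes bias from loss that depends only on baseline fatigue. It does not remove bias from loss that depends on the outcome.
3. **Missing post-tests.** Report numbers lost and reasons by arm. Add a sensitivity analysis that shifts missing study-arm values toward worse fatigue until the conclusion changes.

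**Cost.** Changes to wording and a little more analysis. Patients who stop sessions but still attend the unit for dialysis need no extra visit. Including them may make the estimated effect smaller. Patients who leave the unit or withdraw consent will still be missing, which is why item 3 is needed.

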#### **4.2. Research Design: Prospective**

#### **4.3. Design of the Research**

The population of the research will be hemodialysis patients treated at Adana City Hospital between 30 May 2023 and 30 September 2023. The research sample will consist of patients who meet the research criteria and agree to participate voluntarily in the research. The sample number of the study was calculated using the G\*Power 3.1.9.7 program (25). In the calculation, a sample calculation was made for repeated measures ANOVA test. In the calculation, Cohen's medium effect size ( $f = 0.5$ ), 5% margin of error ( $\alpha = 0.05$ ) and 95% power ( $1-\beta = 0.95$ ) and the correlation value between repeated measurements were taken as 0.50 for each group (study and control). ) sample size was calculated as 21 patients (42 patients in total). Considering the possibility of patients leaving the groups during the research process, the number of samples for each group was increased by 30%, taking into account the possibility of data loss in order not to adversely affect the statistical power, and 30 patients (total of 60 patients) for each group (study and control) were included in the sample planned (26). Randomization in the study will be done on the website of randomizer.org and patients will be included in the study and control groups with the appropriate randomization method according to the dialysis unit list (27).

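### Section 4.3 calls f = 0.5 a medium effect, but for two equal groups it is a one-SD difference (d = 1.0), so the stated 95% power is not power for a medium effect

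*Combined protocol and SAP*

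**What the plan says.** Section 4.3 sizes the trial for a repeated-measures ANOVA. The assumed effect and error rate are given as "In the calculation, Cohen's medium effect size ( $f = 0.5$ ), 5% margin of error", with 95% power, and "the correlation value between repeated measurements were taken as 0.50 for each group". The result is reported as "sample size was calculated as 21 patients (42 patients in total"). This is then raised to 30 per group, 60 in all, to allow for patients who leave.

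The G*Power listing under section 4.3 is headed "F tests - ANOVA: Repeated measures, between factors". It shows 0.5 in the field for effect size f, alpha 0.05, power 0.95, 2 groups, 2 measurements and correlation 0.5. The output is a noncentrality parameter of 14.0, critical F 4.0847 on 1 and 40 degrees of freedom, total N = 42 and actual power 0.9545279.

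No pilot result, published difference or minimal important difference is offered for 0.5. The only support is the adjective, with a power-analysis textbook cited at the end of the sample-size statement. Section 4.1 plans a repeated-measures ANOVA and, for each measurement separately, an independent-samples t-test between groups. Fatigue is the primary outcome, and the scales are completed once before and once after the four weeks of treatment.

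**The concern.** The adjective and the number do not belong together. On Cohen's scale for f, medium is 0.25 and large is 0.40; 0.5 is the medium value on the d scale, which for two equal groups is twice f. The plan therefore attaches 95% power to a medium effect when the calculation was run for an effect twice that size.

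This matters because the adjective is the only description of the effect the trial is meant to detect. As written, section 4.3 tells its reader that 21 patients per group give a 95% chance of detecting a medium effect, and the design lacks that property. Someone who relied on the statement could take a non-significant fatigue result as stronger evidence against a moderate benefit than it would be.

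The point does not depend on which test was selected in G*Power. Under any test, the label and the input disagree.

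**Working it through.** **Inputs.** From section 4.3 and the G*Power listing: f = 0.5, alpha = 0.05, k = 2 groups of equal size, m = 2 measurements, correlation rho = 0.5, N = 42 from the calculation and N = 60 planned. The benchmarks 0.25 (medium) and 0.40 (large) for f, and 0.5 (medium) for d, are the standard convention that the plan invokes by name. The plan does not print them.

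**Scale.** With two equal groups whose means differ by d SDs, each group mean lies d/2 SDs from the overall mean, so f = d/2. Hence f = 0.5 is d = 1.0, and d = 0.5 is f = 0.25.

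**Formula for the plan's test.** lambda = f² × N × m / (1 + (m − 1) × rho), with 1 and N − 2 degrees of freedom; power comes from the noncentral F distribution.

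**Reproducing the plan.** lambda = 0.25 × 42 × 2 / 1.5 = 14.0; critical F = 4.0847; power = 0.9545. All three match the listing. N = 40 gives 0.945, so 42 is the smallest even total that reaches 0.95. The arithmetic is right for f = 0.5.

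**Same calculation, other effect sizes**

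| f | N analysed | lambda | Power |
|---|---|---|---|
| 0.25 | 42 | 0.0625 × 42 × 2 / 1.5 = 3.5 | 44.7% |
| 0.25 | 60 | 0.0625 × 60 × 2 / 1.5 = 5.0 | 59.4% |
| 0.40 | 42 | 0.16 × 42 × 2 / 1.5 = 8.96 | 83.2% |
| 0.40 | 60 | 0.16 × 60 × 2 / 1.5 = 12.8 | 94.0% |

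In this calculation, 95% power at f = 0.25 would need N = 158. Varying the correlation from 0.3 to 0.7 moves the f = 0.25 power from 50% to 40% at N = 42, and from 66% to 54% at N = 60.

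**Post-test t-test (planned in section 4.1), d = 0.5.** Noncentrality = d × √(n/2), with 2n − 2 degrees of freedom, two-sided alpha 0.05.
- n = 21 per arm: 0.5 × √10.5 = 1.620; power 35.3%.
- n = 30 per arm: 0.5 × √15 = 1.936; power 47.8%.

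**Why the two sets of figures differ.** The between-factors test compares the groups on the average of the two measurements, so its f = 0.25 means a half-SD difference on that average. In a randomised trial the expected baseline difference is zero. A half-SD difference at post-test alone is then (0 + 0.5)/2 = 0.25 SD on the average, or f = 0.125. This gives lambda = 0.015625 × 42 × 2 / 1.5 = 0.875 and power 15% at N = 42, and lambda = 1.25 and power 20% at N = 60. A power figure for a medium effect therefore means little unless the test and the effect are named.

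**The case against.** The strongest reply is that nothing was miscalculated. The text, the input field and the noncentrality parameter all use f = 0.5 consistently, the value is disclosed, and if f = 0.5 was intended then 95% power stands for that effect. This is correct. It limits the error to the description of the effect, but that description is the plan's only justification for the value.

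A second reply is that power at f = 0.25 depends on the test. For the group-by-time interaction in G*Power's default parametrisation, f = 0.25 gives 89% at N = 42 and 97% at N = 60. The plan did not size on that test. With two groups and two measurements, that f also means a difference in mean change of 4 × 0.25 = 1.0 SD, so the 89% is again power for a one-SD effect; it equals the t-test at d = 1.0 with 21 per arm (88.5%). It does not rescue the word medium, but it does show that 45% and 59% need their test stated.

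A third reply is that 59% flatters the design. Section 4.3 adds the 60 − 42 = 18 extra patients to cover losses, so 59% requires that nobody drops out. This stands.

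A reader might also infer that the d benchmark was typed into the f field by mistake. That is plausible, but a wrong adjective on an intended f = 0.5 fits the documents equally well. Nor does any passage say how a non-significant result would be interpreted, so misreading is a risk, not something the plan commits to.

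**Conclusion.** The point holds as a mislabelled effect size. The 95% power with 42 patients is for a one-SD difference (d = 1.0), not a medium one. In the plan's own between-factors calculation, with correlation 0.5, f = 0.25 has 45% power with 42 analysed and 59% with all 60 analysed. For a half-SD difference at post-test, the planned t-test has 35% with 21 per arm and 48% with 30. None of these is near 95%.

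The conclusion rests on f = d/2 for equal groups, which is algebra, and on the conventional benchmarks for f. The percentages also rest on the named test, the stated correlation and the number analysed.

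The tempting stronger reading is that the trial's power for a medium effect simply is 45% or 59%. The documents do not support an unconditional figure: those values belong to one test and to a difference present on the average of both measurements. Nor does the point show that 60 patients are too few, because the plan gives no clinically based target difference against which to judge that.

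**What to change.** In section 4.3, replace the description of f = 0.5 as Cohen's medium effect with:

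> *an effect of f = 0.5 (a one-SD difference, d = 1.0, above Cohen's large value of f = 0.40)*

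Then add:

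> *The study is not powered at 95% for a medium effect: for a half-SD difference at post-test, the independent-samples t-test has about 35% power with 21 analysed per group and 48% with 30 (no dropout); the between-factors calculation above with f = 0.25 gives 45% and 59%, and that f assumes the difference is present on the average of both measurements.*

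Enrolment stays at 60, and neither the analysis nor the conduct of the trial changes. The cost is two edits to section 4.3 and a power statement that looks less favourable.

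### Section 4.3 claims 95% power for a medium effect, but f = 0.5 is a 1.0 SD group difference averaged over pre-test and post-test; at f = 0.25 the same run has 45% (N = 42) or 59% (N = 60) power

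*Combined protocol and SAP*

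**What the plan says.** Section 4.3 sizes the trial for a repeated-measures ANOVA. The effect is described as a "medium effect size ( $f = 0.5", with a "5% margin of error", 95% power, and the "correlation value between repeated measurements were taken as 0.50". The result is 21 patients per group (42 in total), raised to 30 per group (60 in total) for dropout.

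The G*Power printout in the same section identifies the test as "ANOVA: Repeated measures, between factors", with two groups and two measurements. It reports a noncentrality parameter of 14.0, critical F 4.0847457 on 1 and 40 degrees of freedom, and actual power 0.9545279.

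The text after the printout gives the timing of the two measurements: "The results will be collected before the acupressure and in the 4th week of the last intervention". Section 5 (Research Flow Process, second step) confirms that the scales are first completed "as a pre-test with an informed consent form".

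Section 4.1 plans two analyses that bear on this: "Differences in repeated measures between groups will be tested with the Repeated Measures test" and "Differences between groups for each measurement will be tested with the Independent Samples t-test". It does not say which effect of the repeated-measures ANOVA is the primary test.

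**The concern.** The word medium is the only justification given for f = 0.5. Section 4.3 offers no pilot data, no standard deviation, no difference in scale points and no earlier estimate for fatigue, the primary outcome. Yet f determines the sample size.

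Two features make the label misleading. First, for two equal groups f is half the standardised difference, so f = 0.5 is a full 1.0 SD. Second, a between-factors test compares group means averaged over all measurements. One of the two is taken before any acupressure, when randomised groups should not differ in expectation, so the whole averaged difference has to come from the post-test.

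The 95% figure is the plan's justification for 42 patients. A reader told that the trial has 95% power for a medium effect would take a null fatigue result as evidence against a moderate benefit. The calculation does not support that inference.

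**Working it through.** **Inputs from Section 4.3 and its printout:** two groups of equal size, m = 2 measurements, correlation ρ = 0.5, α = 0.05, N = 42 or 60. The 60 allow for 30% loss: 60 × 0.70 = 42.

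**Assumption:** conventional medium is f = 0.25 (0.5 SD between two groups). The documents do not state this value, so a range is shown.

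**Step 1. Reproduce the plan's figure.** For the between-factors effect,

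λ = f² × N × m / (1 + (m − 1)ρ), with 1 and N − 2 degrees of freedom.

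At f = 0.5 and N = 42: λ = 0.25 × 42 × 2 / 1.5 = 14.0, critical F = 4.0847457, power = 0.9545279. All three match the printout.

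**Step 2. Translate f.** For two equal groups f = (difference in means) / (2 × SD), so f = 0.5 gives a difference of 2 × 0.5 = 1.0 SD, averaged over both measurements. If the groups are equal at pre-test and differ by D at post-test, the averaged difference is D/2 and f = D/4. So f = 0.5 means D = 2.0 SD, and f = 0.25 means D = 1.0 SD.

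**Step 3. Change only f in the same run.** At f = 0.25:

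- N = 42: λ = 0.0625 × 42 × 2 / 1.5 = 3.5, power 44.7%.
- N = 60: λ = 0.0625 × 60 × 2 / 1.5 = 5.0, power 59.4%.

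| f | Power, N = 42 | Power, N = 60 |
|---|---|---|
| 0.20 | 31% | 42% |
| 0.25 | 44.7% | 59.4% |
| 0.30 | 59% | 75% |
| 0.40 | 83% | 94% |
| 0.50 | 95.5% | 99.3% |

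At f = 0.25 and ρ = 0.3 the powers are 50% and 66%; at ρ = 0.7 they are 40% and 54%. At f = 0.25 and ρ = 0.5 the run would need N = 98 for 80% power or N = 158 for 95%, before dropout.

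**Step 4. A statement that needs no benchmark.** The run reaches 95% power only from f = 0.494 (N = 42) or f = 0.410 (N = 60). With equal baselines, D = 4f, which is about 1.98 SD or 1.64 SD at post-test.

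**Step 5. Compare the planned tests on one scale.** D is the post-test difference with equal baselines. The two-sided post-test t-test has noncentrality (n/2) × D², with n = 21 or 30 per group. For D = 0.5 this is 2.625 or 3.75; for D = 1.0 it is 10.5 or 15.

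| Post-test difference D | t-test, 42 / 60 | Between-factors run, 42 / 60 |
|---|---|---|
| 0.5 SD | 35.3% / 47.8% | 15.0% / 19.6% |
| 1.0 SD | 88.5% / 96.8% | 44.7% / 59.4% |
| D detectable with 80% power | 0.89 / 0.74 SD | 1.54 / 1.27 SD |

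At ρ = 0.5 the change score has variance 2(1 − 0.5) = 1, the same as a single measurement, so the group-by-time test has the same power as the t-test at each D. Simulation with 20,000 trials per setting agreed with the formulas: for D = 1.0, the between-factors test gave 0.447 / 0.597 and the t-test 0.884 / 0.969.

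**The case against.** The strongest reply is that nothing is miscalculated. The plan prints f = 0.5 beside the 95%, and the power is right for that f, so only one word is in dispute. Calling that word wrong relies on a benchmark that the documents do not state. The 45% and 59% also belong to one test, the between-factors effect, which Section 4.1 does not name as primary. For the same 1.0 SD post-test difference, the planned t-test has 88.5% or 96.8% power, and a group-by-time test would match it at ρ = 0.5.

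Much of this stands as a limit on scope. The 45% and 59% describe the documented run, not the trial's power under every planned analysis. The 2.0 SD figure comes from the choice of test and from equal baselines, not from the label.

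It does not rescue the claim. None of the smaller values of f examined, from 0.20 to 0.40, reaches 95% at either sample size, and f = 0.5 is a 1.0 SD averaged difference whatever it is called. For a 0.5 SD post-test difference, the t-test has only 35.3% or 47.8%. The extra 18 patients are a dropout allowance, and with no dropout at all the run still has only 59.4% at f = 0.25.

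One caveat applies to every figure here. All assume individually randomised patients, whereas Section 4 also describes assignment by dialysis day. If allocation were by day, neither the plan's figures nor these would hold.

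**Conclusion.** The concern holds. The printed power of 0.9545 is correct for f = 0.5, but calling that effect medium is unsupported, and the design does not have 95% power for a medium effect as usually understood. At f = 0.25 the documented run has 44.7% power with 42 patients and 59.4% with 60.

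These two figures rest on the assumed convention of f = 0.25, ρ = 0.5 and individual randomisation; the 59.4% also assumes no dropout. That f = 0.5 is a 1.0 SD averaged difference follows from the plan's own inputs without any benchmark. The 2.0 SD post-test equivalent adds only equal baselines.

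**What to change.** Keep N = 60. In Section 4.3, delete the word medium and replace the power statement with text such as:

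> The calculation assumes f = 0.5 in the between-factors test, that is, a group difference of 1.0 SD averaged over pre-test and post-test (2.0 SD at post-test if baselines are equal) [cite fatigue data if they exist]. At f = 0.25 (0.5 SD averaged; 1.0 SD at post-test) the same calculation gives about 45% power with 42 completers and 59% with 60. Sensitivity, as the post-test difference with equal baselines and a correlation of 0.5: for 0.5 SD, the post-test t-test has about 35% (42) or 48% (60) power and the between-factors test about 15% or 20%; for 1.0 SD, the t-test has about 89% or 97% and the between-factors test about 45% or 59%. The post-test difference detectable by t-test with 80% power is about 0.89 SD (42) or 0.74 SD (60).

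If space is short, the essential parts are the meaning of f = 0.5, the power at f = 0.25, and the difference detectable by t-test.

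The cost is about four sentences, with no added patients and no change to the planned tests. The downside is a less favourable power statement.
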